5.8 Criteria for diagnosis

Acute respiratory viral infection (ARVI) is an acute, local (in most cases) respiratory tract infection presenting with catarrhal inflammation of the upper respiratory tract and proceeding with fever, runny nose, sneezing, cough, sore throat, a violation of the general condition of different manifestations.

The patient or parents (legal representatives) may complain of acute rhinitis and / or cough and / or conjunctival hyperemia (catarrhal conjunctivitis) in combination with symptoms of rhinitis, pharyngitis. The disease usually begins acutely, often accompanied by an increase in body temperature to subfebrile values (37.5 °C — 38.0 °C). Febrile fever is more typical for influenza, adenovirus infection, and enterovirus infections. Elevated temperature in 82% of patients is reduced by the 2-3rd day of the disease; longer (up to 5-7 days) febrile is maintained during influenza and adenovirus infection [7]. An increase of fever intensity during the disease period, or appearance of severe intoxication symptoms may indicate the accession of a bacterial infection. Repeated raise of temperature after a short-term improvement often related to development of acute otitis media following the long-lasting runny nose.

Nasopharyngitis is characterized by complaints of nasal congestion, discharge from the nasal passages, nasopharynx discomfort: burning, tingling, dryness, often accumulation of mucous discharge, which in children, flowing down the posterior pharyngeal wall, can cause a productive cough. When inflammation spreads to the mucosa of auditory tubes (Eustachitis), clicking, noise and ear pain may occur, and a sense of hearing may decrease. Clinical course of nasopharyngitis has the following age features: in infants - fever, discharge from the nasal passages, sometimes - anxiety, difficulty in feeding and falling asleep. In older children, the typical manifestations are rhinitis symptoms (peak on day 3, duration up to 6-7 days), in 1 / 3-1 / 2 patients - sneezing and / or cough (peak on day 1, average duration - 6-8 days), rarely - headache (20% in the 1st and 15% - up to the 4th day) [8].

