11. SAFETY ASSESSMENT

The safety of compared drugs will be assessed throughout the study on the occurrence and development of adverse events (AE) recorded primarily on the complaints of patients, as well as on the data of physical examination and the results of laboratory and instrumental examination.

Adverse event - any medically unfavorable event observed in the subject of the study after the use of the medicinal product, which may not have a causal relation with its use.

³ Axillary body temperature > 37.0 °C confirmed by two measurements (morning-evening/evening-morning)

Thus, an adverse event (AE) can be any unfavorable symptom (including deviation of the laboratory value from the norm), a complaint or a disease, the time of occurrence of which does not exclude a causal relationship with the use of the medicinal (test) product, regardless of the presence or absence of such communication.

The severity of AE is established in accordance with the following classification:

- Grade 1 (mild AE): an adverse event easily tolerated by the patient, causing minimal discomfort and not interfering with daily activities;
- Grade 2 (moderate AE): an adverse event that causes discomfort that interferes with daily activities;
- Grade 3 (severe AE): an adverse event that interferes with normal daily activities.

The AE relation to the product prescription is determined by the WHO scale:

Certain. Clinical manifestation of AEs, laboratory findings deviations occur during the period of administration of the product are unlikely to be explained by the presence of existing diseases and other factors. Manifestations of AEs regress after the product discontinuation and occur again after repeated administration.

Probable. Clinical manifestations of AEs, laboratory findings deviations have temporal association with the product administration, are unlikely to have any association with concurrent diseases or other factors, and which regress upon cancellation of the product. Response to the drug re-challenge is unknown.

Possible. Clinical manifestation of AEs, changes in laboratory findings have temporal association with the product administration, but they can be explained by the presence of concomitant diseases or administration of other medicinal products and the influence of chemical compounds. Information on drug withdrawal response is unclear.

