11.1 Methods and terms of analysis safety parameters recording

The presence of adverse events is assessed according to the patients' complaints, as well as according to the physical examination and the results of laboratory and instrumental examination. Investigators are responsible for identifying, providing necessary medical care, documenting and reporting cases that fall within the definition of AE and SLEEP.

For safety assessment, the following laboratory parameters are determined according to the schedule of Visits (Visit 0 (Screening), Visit 3 (Day 8 ± 1)):

- Clinical blood test;
- Common urine analysis.

Laboratory deviations

Any clinically significant abnormalities in the clinical blood count, clinical urine analysis will be evaluated by the Investigator. In case of significant deviations of laboratory parameters on Visit 3 (day 8 ± 1) in comparison with the initial parameters at Visit 0 (screening), it is necessary to conduct additional laboratory monitoring before normalizing or determining the cause of the deviation.

Any additional laboratory control is carried out by the Investigator's decision. Any clinically significant laboratory deviation shall be documented as AE in the patient's medical record and in the CRF unless the deviation is due to laboratory error; in this case, a corresponding note shall be made in the primary documents.

General medical history and anamnesis morbi

General information about the medical history and anamnesis morbi is collected on the screening visit and includes:

- date of disease onset;
- previous and concurrent diseases, and surgery in the previous 6 months prior to the study inclusion;
- concomitant therapy (drug products, other treatments) and products used for 6 months prior to the study inclusion;
- smoking, alcohol and narcotic drug abuse.

Physical examination

A general physical examination is conducted on Visit 0 (Screening), Visit 1 (Day 1), Visit 2 (Day 3), Visit 3 (Day 8 ± 1). Clinically significant changes on visits - Visit 1 (Day 1), Visit 2 (Day 3), Visit 3 (Day 8 ± 1), absent on Visit 0 (Screening) are regarded and documented as AE in the patient's medical record and in the CRF.

Major vital signs

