On Visit 0 (Screening), Visit 1 (Day 1), Visit 2 (Day 3), Visit 3 (Day 8 ± 1), the following basic vital signs are measured: HR, RR, body temperature. Clinically significant changes on visits - Visit 1 (Day 1), Visit 2 (Day 3), Visit 3 (Day 8) absent on Visit 0 (Screening) may be regarded as AE, depending on the clinical situation, at the discretion of the study physician; in this case, they are documented in the patient's medical record and in the CRF.

ECG

12-lead ECG can be performed on Visit 0 (Screening), only if there is a suspicion of cardiovascular pathology.

11.2 Requirements to reports, procedures for recording adverse events and intercurrent diseases and requirements for notification of regulatory authorities

When studying the efficacy of Polyoxidonium®, nasal and sublingual spray, 6 mg / ml (NPO Petrovax Pharm, Russia), a mandatory requirement is the concomitant assessment of the safety and tolerability of the studied doses in patients with a specific disease for whom this drug is being developed (in this case for children aged 1 to 12 years).

The presence and severity of adverse events after taking the investigated drugs will be assessed according to the complaints of patients and / or their parents / adoptive parents, physical examination data and the results of laboratory and instrumental examinations. At the same time, during observation of patients, known AEs related to the use of drugs with the active substance of Azoximer bromide and described in the current instructions for use of the drug Polyoxidonium® (section 5.2) will be especially taken into account.

The Investigator is responsible for notifying the Sponsor of any event that seems unusual, even if this event may be considered as an unexpected benefit to the patient.

All AEs that will occur with the patient after the first dose of the investigational drugs in the indicated dose will be registered.

With the development of any adverse events, the Investigator must record the case in the patient's medical record and fill in the appropriate pages of the CRF, assess the feasibility of continued patient's study participation. Adverse events will be registered from the time of the first use of the drug until the completion of the study.

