As a result of calculation based on the above values ($Z\alpha=1.645$, $Z\beta=0.842$, $SD=0.2$ day, $\delta=-0.52$ day, $\mu_o=2.6$ days, and $\mu_p=3.2$ days), the sampling size was obtained that ensures a statistical study power of at least 80%, equal to 78 patients in each group (156 subjects in total). Taking into account the dropout of patients at screening, it is planned to obtain Permission of the Ministry of Health of the Russian Federation to screen 210 patients, of whom 172 will be randomized.

Patients enrolled in the study will be randomized to one of two groups using Polyoxidonium® or placebo.

12.2 Description of the statistical methods to be used, including terms of each interim analysis

Given the main study purposes (efficacy and safety assessment), the main tools for the analysis will be descriptive statistics and graphical representations.

Continuous (quantitative) variables will be tabulated using such parameters of summary statistics as the amount of data, the amount of missing data, mean, standard deviation, median, Q_1 and Q_3 , minimum and maximum values.

The descriptive statistics and tables will be presented for all demographic and baseline data. Baseline demographic characteristics, medical history and examination data are the most recent data recorded before the first product use. A comparative analysis of these data will be carried out in a population of patients who have undergone all the study procedures and completed it according to the Protocol (per-protocol (PP) population). Based on the results of efficacy analysis, the comparative statistics will be presented. Comparison of quantitative indicators satisfying the conditions of normal distribution and equality of variances will be carried out by Student's t-test. Comparison of quantitative indicators not satisfying the conditions of normal distribution and equality of variances will be carried out by Mann-Whitney test. To compare the paired quantitative indicators satisfying the conditions of normal distribution and equality of variances, the paired Student's t-test will be used; for those not satisfying the conditions of normal distribution or equality of variances - the paired Wilcoxon test. A comparative analysis of qualitative variables will be carried out by Chi-square test; if more than 20% of the expected frequencies are less than 5, the exact Fisher's two-tail test will be used.

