The efficacy data analysis will be carried out in a population of patients who have undergone all the study procedures and completed it according to the Protocol (PP population). The safety population will consist of all patients who have received at least one dose of the study product, for which further safety surveillance data is provided (ITT population). The safety parameters evaluated during the study include the results of patient's general condition assessment, measurements of vital signs, a general physical examination, patient's examination, a clinical blood test, and urinalysis (compared to baseline values on Visit 0).

Throughout the study the following will be recorded:

- All study product related cases of AEs and SAEs (number, severity).
- All cases of early study termination due to the development of AEs/SAEs associated with the study product administration (number, severity).
- Local adverse reactions (number, severity, connection with the product). Safety parameters will be studied descriptively for each group.

The number of AEs and patients with AEs will be summarized by treatment groups, with a distribution by systems and selected terminology. Additional generalizations will be made on the severity, as well as the connection with the study product.

Early withdrawn patients will be presented in the Patients List and summarized by the main reason for withdrawn, and by each treatment group. Indicators of physiological functions and laboratory analyzes at the baseline (Visit 0), as well as their changes from the baseline (Visit 3), will be summarized by treatment groups. In addition, the tables of changes in laboratory analyzes based on the classification of values as low, normal or high, relative to the norm limits, will be summarized and presented by treatment groups.

Not available or missing data will not be replaced.

In addition to the standard summary analysis, the Sponsor may conduct the additional analyzes, if deemed necessary.

Interim analysis An interim analysis was not planned.

Groups for analysis

Safety population and Per-Protocol Population.

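### Section 11.1 judges adverse events against Visit 0 rather than the last pre-dose assessment, so when Visits 0 and 1 are separate, signs that arose before dosing can be counted as adverse events (minor)

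*Combined protocol and SAP*

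**What the plan says.** - **Section 11.1, physical examination.** The rule covers "Clinically significant changes on visits - Visit 1 (Day 1), Visit 2 (Day 3), Visit 3 (Day 8 ± 1), absent on Visit 0" and is mandatory: such changes, if "absent on Visit 0 (Screening) are regarded and documented as AE in the patient's medical record and in the CRF".
- **Section 11.1, vital signs.** The visits and the Visit 0 reference are the same, but a change only "may be regarded as AE, depending on the clinical situation, at the discretion of the study physician".
- **Section 11, definition.** An adverse event is "any medically unfavorable event observed in the subject of the study after the use of the medicinal product".
- **Section 11.2, window.** "Adverse events will be registered from the time of the first use of the drug until the completion of the study". The synopsis (statistical methods) and section 7.1 also tie safety recording to the first use of the product.
- **Section 12.2, baseline.** For demographic, history and examination data, "examination data are the most recent data recorded before the first product use". Later in the same section the reference for change is Visit 0: "Indicators of physiological functions and laboratory analyzes at the baseline (Visit 0" is the stated starting point for both vital signs and laboratory values.
- **Section 9.1.2, order at Visit 1.** Physical examination and vital signs belong to the eligibility re-check. Randomisation follows, then the first dose, then one hour of observation for adverse events. If Visits 0 and 1 are combined, the examination and vital signs are not repeated.
- **Section 12.4.** AE incidence is compared between arms with Fisher's exact test.

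**The concern.** A child is screened within 24 hours of the first symptoms, while the illness is still developing. Section 5.8 describes, in older children, "rhinitis symptoms (peak on day 3, duration up to 6-7 days". If Visit 1 is a separate contact, new nasal or throat signs or a higher temperature may already be present at its examination, before any product is given. Section 11.1 tells the site to enter a clinically significant new examination finding as an AE, although treatment cannot have caused it.

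Two things are at stake. The first is the between-arm AE comparison, which would carry the same untreated background in both arms and be less able to show a real difference. The second is the summary of vital-sign change, which would mix pre-dose change with change on treatment. Temperature matters here because section 5.2.1 lists a possible rise in body temperature as a side effect of the product.

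**Working it through.** The documents state no figure on this point, so the main check is to set the sections side by side.

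**1. Visits combined.** Under 9.1.2 the examination is done once. No change from Visit 0 to Visit 1 can exist, and Visit 0 is the last pre-dose assessment. Sections 11.1 and 12.2 agree, and exposure is zero.

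**2. Visits separate, finding first seen at the Visit 1 examination.** Section 11.1 makes it an AE. The definition in section 11 and the window in 11.2 do not, because no product has been used. A site cannot comply with both.

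**3. Visits separate, same finding still present on Day 3 or Day 8.** It was absent at Visit 0, so 11.1 again makes it an AE, now recorded at Visit 2 or 3. At that point it is observed after use of the product and falls inside the registration window. The first-dose rules no longer clearly remove it. Only a reference to the last pre-dose assessment does.

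**4. Is there a later filter?** Section 12.4 summarises all adverse events together and compares their incidence, with no onset rule. The synopsis speaks of events reported after first use, which concerns reporting rather than onset. The corresponding list in 12.2 instead refers to product-related events.

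**5. Illustration of dilution.** All rates here are assumed.

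- 86 children per arm (172 randomised, 1:1).
- True post-dose AE incidence p of 20% and 5%.
- A share q of both arms with a pre-dose finding counted as an AE, independent of true AEs.
- Two-sided Fisher's exact test at 0.05, with power by exact enumeration.

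Counted incidence = 1 − (1 − p)(1 − q). The difference between arms becomes 0.15 × (1 − q). For q = 10%: 1 − 0.80 × 0.90 = 28.0%; 1 − 0.95 × 0.90 = 14.5%; difference 13.5 percentage points.

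| q | Children affected (172 × q) | Counted incidence | Ratio | Power |
|---|---|---|---|---|
| 0% | 0 | 20.0% vs 5.0% | 4.0 | 83% |
| 2% | 3.4 | 21.6% vs 6.9% | 3.1 | 75% |
| 5% | 8.6 | 24.0% vs 9.8% | 2.5 | 65% |
| 10% | 17.2 | 28.0% vs 14.5% | 1.9 | 51% |
| 20% | 34.4 | 36.0% vs 24.0% | 1.5 | 35% |
| 30% | 51.6 | 44.0% vs 33.5% | 1.3 | 24% |

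With both arms at the lower counted incidence, the type I error runs from 1.8% (q = 0%) to 3.4% (q = 30%). The distortion is loss of sensitivity, not false signals. The rows at 20% and 30% show the shape of the effect; nothing in the documents suggests that shares of that size are likely.

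**The case against.** The strongest reply is that the other rules already exclude pre-dose findings. The definition, the 11.2 window, the synopsis and 7.1 all start at first use; 11.1 itself asks investigators to report cases that meet the AE definition; and section 11 has the start of each event recorded, so pre-dose onset could be identified. **This stands against the stronger inference that AE counts will include events that cannot be due to treatment.** The documents support only that they can. It does not dispose of step 3, because no section says that a persisting sign must be screened by its onset.

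Other parts of the reply also stand:

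- Exposure is short. Enrolment is limited to 24 hours from symptom onset and eligibility is re-checked at Visit 1, so the gap is about a day at most. Much of the evolution towards a day-3 peak falls after dosing, and no change of baseline would remove it.
- Only clinically significant changes count, and a child who has become ineligible by Visit 1 is not dosed.
- Section 7.1 rests the safety conclusion on events with at least a possible relation to the product, which gives some insulation. The Fisher comparison in 12.4 is not limited in that way.
- Laboratory baseline is not in conflict: Visit 0 is the only pre-dose sample.
- Vital-sign changes are presented descriptively, and the vital-sign AE rule is discretionary.
- Striking Visit 1 from 11.1 altogether could lose findings from the hour of observation after the first dose.

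A reader might also infer from the power table that a real safety difference would be hidden. The documents give no AE rates, no share of separate visits and no planned power for safety, so that inference is not supported.

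**Conclusion.** The inconsistency is real and minor. With separate visits, the Visit 0 reference in 11.1 cannot be reconciled with the AE definition, the registration window or the pre-dose baseline in 12.2. A site that follows it literally can enter pre-dose signs of ARVI as AEs, either at Visit 1 or, less visibly, when they persist to Visit 2 or 3. Randomisation should balance such findings between arms, so the effect is non-differential dilution. Its size cannot be derived from the documents and is zero if the visits are always combined.

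**What to change.** - **Section 11.1.** For physical examination and vital signs, make the reference the last assessment before the first dose (Visit 1, or Visit 0 when the two are combined). Count as AEs only findings with onset or worsening after the first dose, and say that this includes findings from the one-hour observation at Visit 1. The discretion for vital signs can remain.
- **Sections 12.2 and 12.4.** Use the same baseline for vital-sign changes. Keep Visit 0 for laboratory values. State the onset rule for the AE tables and the Fisher comparison.
- **Recording.** Enter changes between Visit 0 and the first dose as pre-treatment findings, not as AEs.

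The cost is minor rewording and a check of onset times against the time of the first dose. No new assessments are needed.

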8.1 Inclusion criteria

A patient shall meet the following inclusion criteria:

1. Patients of both sexes aged 1 to 12 years inclusive.
2. Diagnosis of ARVI [ICD-10 code: J00 - Acute nasopharyngitis (runny nose), J02 - Acute pharyngitis, J02.9 - Unspecified acute pharyngitis, Acute laryngitis and tracheitis - J04, J04.0 - Acute laryngitis, J04.1 - Acute tracheitis, J04.2 - Acute laryngitis, Acute upper respiratory tract infections of multiple and unspecified localization - J06, J06.0 - Acute laryngopharyngitis, J06.9 - Acute upper respiratory tract infection, unspecified] confirmed by physician's examination: axillary temperature ≥ 37.0 °C (measured at the moment of physical examination) and Symptom Assessment Scale total score ≥ 5 points, not less than 3 of which should be related to ENT-organs and upper respiratory tract affection (accord. the Symptom Assessment Scale [Appendix 1]).
3. Not more than 24 hours from the onset of ARVI manifestations.
4. Signing an Informed Consent Form by one of the parents/adoptive parent of the child and the child him/herself (if aged ≥ 10 years);

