9.1.6. Description of study procedures

Demographic and anthropometric data collection

Demographic data include date of birth, age (number of full years at the time of participation in the study), gender and race. Anthropometric data include weight and height.

Medical history collection

The medical history data includes a description of the underlying disease, including the duration and effect of previously received therapy, a description of previous and concurrent diseases. In addition, information about concomitant therapy shall be collected: INN, trade name, strength, presentation, single and daily dose, date of therapy initiation and termination.

Physical examination

Physical examination includes an examination of the following organs and systems:

- Skin, hair, nails
- Endocrine system
- Cardiovascular system
- Respiratory system, state of nasal passages, character of discharge
- Gastrointestinal tract, including oral examination using a spatula and flashlight
- Nervous system
- Musculoskeletal system
- Reproductive system
- Urinary system

Measurement of vital signs

Measurement of HR, RR shall be performed by qualified medical personnel in accordance with the standards adopted at the study site.

The study is conducted as part of the safety assessment of study subjects.

Body temperature measurement.

It is conducted at screening visits, Visit 1, 2 and 3 by medical personnel, and at home by parents/adoptive patients.

Algorithm for measuring body temperature:

1. Wash your hands with warm water and soap
2. Inspect the armpit, and wipe it dry

3. Take a thermometer and shake off mercury below 35 °C
4. Position the thermometer in the armpit so that the measuring tank is in contact with the body from all sides
5. Measure the temperature for 10 min
6. Pay attention to between the body and the thermometer was no linen
7. Remove the thermometer and record the digital data
8. Shake the thermometer

Parents/adoptive parents should be instructed on how to conduct thermometry at Screening.

ECG

It shall be conducted at suspicion on cardiovascular disease. At least an hour before the procedure, it is necessary to exclude the outdoor games and emotional stress of the child. No less than 1.5 hours shall pass after the meal. In young children, special electrodes are used, which are tightly fixed on the skin without damaging it. Record at least 10–15 cardiac cycles, and if they are suspicion on of arrhythmia, there may be more cycles.

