12.4 Safety data analysis

Safety population will be evaluated for all types of safety analysis.

Preferred terms of MEDDRA dictionary (Preferred Term) will be used for coding and presenting the Lists of adverse events and associated diseases. All adverse events in the aggregate, as well as serious adverse events, adverse events associated with the therapy, and on other significant adverse events (for example, on adverse events that led to the cancellation of study therapy) will be presented through descriptive statistics.

Comparison of treatment groups by the incidence of AEs will be carried by Fisher's exact test.

Clinical laboratory evaluations together with indication of changes from baseline will be presented through descriptive statistics for each visit.

Laboratory deviations beyond normal values will be marked. Lists and summary descriptions of clinically significant hematological laboratory abnormalities will be presented.

Vital signs together with indication of changes from baseline will also be presented through descriptive statistics for each visit.

For a statistical analysis of quantitative indicators, a preliminary assessment of compliance with the law of normal distribution according to the Shapiro-Wilk criterion will be made. When verifying statistical hypotheses, parametric criteria will be used for indicators with a normal distribution, and non-parametric criteria will be used for indicators which distribution differs from normal. Comparison of groups by quantitative indicators will be carried out by Student's t-test for independent samples in the case of a normal data distribution or the Mann-Whitney test in the case of a distribution other than normal. Comparison of indicators within the group between visits will be performed by T-test for related samples in the case of a normal data distribution, or the Wilcoxon test in the case of a distribution other than normal.

To describe the quantitative variables, the use of the following characteristics is planned: mean, standard deviation, median, quartile, minimum, maximum, coefficient of variation.

Qualitative variables will be analyzed by Pearson χ^2 test or Fisher's exact test (if the absolute frequency of the indicator is 5 or less in at least one of the subgroups). To describe categorical data, the use of percentages or shares is planned.

Differences at $p < 0.05$ will be considered statistically significant.

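### New ARVI signs found on examination at Visit 2 must be recorded as AEs and enter the Fisher comparison of AE incidence, which costs power and, if the product works, can mask an excess

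*Combined protocol and SAP*

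**What the plan says.** Section 11.1 has three recording rules.

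- **Physical examination:** clinically significant changes at Visits 1, 2 and 3 "absent on Visit 0 (Screening) are regarded and documented as AE in the patient's medical record and in the CRF". This is mandatory.
- **Vital signs, including temperature:** such changes "may be regarded as AE, depending on the clinical situation, at the discretion of the study physician".
- **Laboratory:** a clinically significant deviation "shall be documented as AE in the patient's medical record and in the CRF unless the deviation is due to laboratory error".

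The general definition in Section 11 covers "any medically unfavorable event observed in the subject of the study after the use of the medicinal product", whatever the cause. None of these texts says how expected signs of the ARVI itself are to be handled.

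The entry condition in Section 8.1 is "Not more than 24 hours from the onset of ARVI manifestations". Section 5.8 says of older children that "the typical manifestations are rhinitis symptoms (peak on day 3, duration up to 6-7 days". The examination described in Section 9.1.6 includes "Respiratory system, state of nasal passages, character of discharge", and also the mouth. Section 12.4 adds: "Comparison of treatment groups by the incidence of AEs will be carried by Fisher's exact test".

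Sections 12.2 and 12.4 also provide tables by system and term, severity and relation to the product, with therapy-associated AEs shown separately. Section 7.1 bases the safety conclusion on AEs with at least a possible relation.

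**The concern.** Enrolment comes early in the illness, and Visit 2 comes when some signs may still be developing. A clinically significant nasal or throat sign that was not there at Visit 0 must then be written up as an AE, even if the investigator sees it as the ordinary course of the infection. At the same visit the physician completes the Symptom Assessment Scale, whose items include nasal discharge, congestion, sneezing, hoarseness, sore throat and cough. One sign can thus appear on the efficacy instrument and in the AE count.

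Two things are at stake in the all-AE Fisher test. Disease events common to both arms make a true product excess harder to see. And if the product does what the trial hopes to show, the active arm will have fewer disease events, which offsets any excess of product-related events. A crude result near equality could then be read as reassurance when it is not.

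**Working it through.** **Number available to the test.** The plan's formula gives n = (1.645 + 0.842)² × 2 × 0.2² / (2.6 − 3.2 + 0.52)² = 77.3, so 78 per group, as stated. Adding 10% gives 78 × 1.1 = 85.8, so 86 per group, also as stated. The safety population can therefore hold up to 86 per arm. The plan states no AE rate and no power for the AE comparison.

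**Is a new sign at Visit 2 foreseeable?** Section 8.1 puts entry within 24 hours of onset, so Day 3 of therapy is about day 3 or 4 of the illness. Section 5.8 puts the rhinitis peak of older children on day 3. A child who enters with, say, sore throat and cough can have nasal signs by Visit 2 that were absent at Visit 0.

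**Model (assumptions).** Let p be the risk of a product-type AE and b the risk of a disease-course AE, independent of each other. A child has any AE with probability 1 − (1 − p)(1 − b). Take p = 12% on active and 2% on placebo, and the two-sided Fisher test at p < 0.05 with 86 per arm. Power is computed by full enumeration.

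*Same background in both arms:*

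| b | Active | Placebo | Difference (points) | Power |
|---|---|---|---|---|
| 0% | 12.0% | 2.0% | 10.0 | 67% |
| 5% | 16.4% | 6.9% | 9.5 | 42% |
| 10% | 20.8% | 11.8% | 9.0 | 29% |
| 20% | 29.6% | 21.6% | 8.0 | 17% |
| 40% | 47.2% | 41.2% | 6.0 | 10% |

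The difference shrinks to 10 × (1 − b) points while the variance grows. Most of the power is lost at low background. Other assumed excesses behave alike: 20% against 5% gives power of 83%, 51% and 35% at b = 0, 10% and 20%; 10% against 0% gives 87%, 32% and 18%. With no product effect, the actual size of the test is 3% to 4% at backgrounds from 10% to 70%, so type I error is not inflated.

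*Lower background on active (same 12% against 2%):*

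| b active / placebo | Active | Placebo |
|---|---|---|
| 15% / 20% | 1 − 0.88 × 0.85 = 25.2% | 1 − 0.98 × 0.80 = 21.6% |
| 10% / 20% | 1 − 0.88 × 0.90 = 20.8% | 21.6% |
| 30% / 40% | 1 − 0.88 × 0.70 = 38.4% | 1 − 0.98 × 0.60 = 41.2% |

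A 5-point reduction in disease events cuts the 10-point excess to 3.6 points. A 10-point reduction turns its direction round in both examples.

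**The case against.** The case against has real force on scope.

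- **The rule is narrower than it may look.** A reader might infer that every clinically significant new finding becomes an AE. The mandatory sentence covers the physical examination only. Vital signs are left to discretion, and laboratory findings have their own rule.
- **A peak is not necessarily a new sign.** Entry needs a symptom score of at least 5, with at least 3 points from ENT and upper respiratory signs. Many signs are thus present at Visit 0, and worsening of a sign already present does not clearly meet the rule. The investigator's judgement of clinical significance filters further.
- **The supporting text is limited.** The day-3 peak is given for older children. The same sentence puts the peak of sneezing and cough on day 1. Rhinitis lasting up to 6–7 days is largely over by Visit 3, so there is little support for new expected signs at that visit.
- **The plan already separates AEs to some degree**, by term, severity and relation. Its safety conclusion rests on at least possibly related events.

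All of this stands as a limit on size. It does not remove the point. The tables are descriptive, whereas the stated between-group test is on AE incidence. The relation filter is also leaky: Section 11 defines a possible relation as one with a temporal link that concomitant disease can explain, which a new ARVI sign during dosing can fit. And even a 5% background lowers power from 67% to 42% in the main example.

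**Conclusion.** The point holds in limited form. Section 11.1 sends new, clinically significant ARVI examination signs into the AE count, and Section 12.4 compares that count without a planned comparison that leaves them out. An equal background lowers power but leaves the test valid. A background reduced by the product can mask an excess or reverse its direction.

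The size is not known. It rests on assumed product-type rates, an assumed background and independence between the two. A reader might infer that disease events will swamp the AE comparison, or that the trial will hide harm. The documents do not support that: they give no AE rates, nothing in them points to a background as high as 40%, and reversal needs a further assumption about benefit. Support is partial at Visit 2 and thin at Visit 3. The remedy is cheap, so the change should be made.

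**What to change.** 1. Keep recording all AEs, and keep the all-AE Fisher test in Section 12.4.
2. In Section 11.1, add a CRF flag, completed by the blinded investigator, for new signs judged to be the expected course of the ARVI.
3. In Section 12.4, specify before unblinding a second Fisher comparison, of AEs not so flagged.
4. Local adverse reactions (Section 12.2), temperature elevation, complications, and any nasal, throat or oral event that starts in close relation to dosing stay in the second comparison whatever the flag says. State in advance what counts as close. A list that simply removed all Appendix 1 items would be wrong, because those items are also plausible local reactions to a nasal and sublingual spray.
5. Report AEs of the Appendix 1 type by arm in their own row, so that local irritation remains visible.
6. Reconcile the mandatory examination rule with the discretionary vital-sign rule, since the two can classify the same disease progression differently.

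**Cost:** one CRF flag, one extra table, and some misclassification between local irritation and ARVI signs. The all-AE test and the separate row limit the harm from the last. No record is lost.
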